7.3 Definition of the MTD and Recommended Phase II Dose

Dose escalation will proceed according to the schema outlined in Table 4. The maximum tolerated dose (MTD) is defined as the highest dose level at which $< 33\%$ of evaluable subjects experienced DLT, when at least 6 patients were treated at that dose level. The MTD will be considered the recommended phase II dose (RP2D), however the principal investigator may ultimately choose a lower dose level as the RP2D, depending on toxicity considerations, dose reduction on subsequent cycles, and other considerations.

7.4 Replacement of Subjects

During the Phase I dose escalation portion of the study, subjects will be replaced for any of the following:

- Missed 30% or more doses of vorinostat during the DLT period (not due to DLT).
- Did not receive the dose of pembrolizumab during the DLT period.
- Study drug discontinuation for any reason other than DLT during the DLT period.

Subjects who are replaced for missed doses may continue to receive study treatment if there is clear clinical benefit, but will not be included in DLT analysis.

During the expansion cohort portion of the study, subjects who discontinue study therapy prior to the first tumor response assessment for a reason other than progressive disease will be replaced.

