3.1 Primary Objectives

- To assess the safety and tolerability of vorinostat plus pembrolizumab therapy by evaluation of toxicities including: type, frequency, severity, attribution, time course and duration.
- To determine the maximum tolerated dose (MTD) and the recommended phase II dose (RP2D) of vorinostat when given in combination with pembrolizumab.

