7.1.1 Treatment Duration

Study treatment will continue until the subject completes 24 months of treatment with the study regimen, or experiences radiographically-confirmed PD (Section 9.2.6 and Section 9.2.6.1), unacceptable adverse experiences, either DLT (Section 7.2) or other unacceptable toxicity (section 10.2), or meets other criteria for study withdrawal or treatment discontinuation

7.1.2 Rules for Phase I Dose Escalation, De-Escalation and Expansion: Adapted Rolling 6 Design

This phase I trial will employ a modified Rolling 6 design, a more conservative version of the Rolling 6 design of Skolnik, et al²⁹. In this design, at most, 3 patients will be under observation for DLT on the current test dose level at any time. Patients who are not evaluable for DLT will be replaced. Once each patient is evaluable for toxicity and passes without a DLT, an additional patient *may* be accrued on that dose level – up to 6 patients. Once 3 patients are evaluable with no patient at that dose level experiencing a DLT, the dose can be escalated, or up to 3 additional patients may be treated at the current dose level. Although this design does not require that 6 patients be treated, no more than 6 evaluable patients will be accrued to any dose level during the dose finding portion of this study. If at any time, the dose level has 1 documented DLT with fewer than 6 evaluable patients, accrual will continue until 6 patients are evaluable. Escalation will terminate as soon as two or more patients experience any DLT attributable to the study treatment, at a given dose level. MTD will be declared at the highest dose level at which 6 patients have been treated and at most 1/6 patients experiences DLT. If more than 1/6 patients experiences DLT, then the next lower dose will be expanded. There will be no intrapatient dose escalation. These rules are outlined in Table 4:

Table 4. Dose Escalation Rules

# Patients on Current Level			Action
With DLT [^]	Evaluable	Evaluable + At Risk [^]	
0	0	1-2	Accrue next patient at this level*
0	0	3	Hold accrual
0	1	1-3	Accrue next patient at this level
0	1	4	Hold accrual
0	2	2-4	Accrue next patient at this level
0	2	5	Hold accrual
0	3-6	3-6	Accrue next patient at the next higher level* ^{+,+}
1	1	1-2	Accrue next patient at this level
1	1	3	Hold Accrual
1	2	2	Accrue next patient at this level
1	2	3-4	Hold accrual
1	3-5	3-5	Accrue next patient at this level
1	3-5	6	Hold accrual
1	6	6	Accrue next patient at the next higher level*

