7.7.1 Vorinostat Dose/Delay Modification Guidelines

Note: If vorinostat is dose-reduced or held for toxicity, and the toxicity is most likely attributed to vorinostat and not attributed to pembrolizumab, administration of pembrolizumab can continue.

Vorinostat dose reductions are NOT permitted during the DLT period. Following the completion of the DLT period, the vorinostat doses may be modified for toxicity according to the below guidelines in Tables 6 and 7. Vorinostat dose delays are permitted during the DLT period due to study treatment-related toxicity, however, if a patient misses > 30% of the vorinostat doses due to toxicity, this will be considered a DLT.

Table 6. Vorinostat Dose Reduction Guidelines

Vorinostat Dose Reductions				
Starting dose	1 st dose reduction	2 nd dose reduction	3 rd dose reduction	4 th dose reduction
Dose Level 1	Dose Level -1	Dose Level -2	Dose Level -2 schedule but 100mg daily	N/A**
Dose Level 2	Dose Level 1	Dose Level -1	Dose Level -2	Dose Level -2 schedule but 100mg daily

mg = milligrams; po = orally; BID = twice daily

**Patients requiring a dose reduction to below 100 mg daily of vorinostat at dose level -2 schedule will discontinue vorinostat permanently.

Table 7. Vorinostat Dose Delay Guidelines

Grade of Event	Management/Next Dose for Vorinostat
≤ Grade 1	No change in dose.

Grade 2	If tolerable to patient, no change needed but monitor patient more frequently. If intolerable to patient, hold* drug until toxicity \leq Grade 1 then resume drug at same dose.
Grade 3 (1 st occurrence)	Hold* until \leq Grade 1. Resume at same dose.
Grade 3 (after 1 st dose reduction)	Hold* until \leq Grade 1: if toxicity related to drug, resume at 1 dose lower; if toxicity not related to drug, resume at same dose or 1 dose lower.**
Grade 3 (subsequent occurrences)	Hold* until \leq Grade 1: if toxicity related to drug, resume at 1 dose lower; if toxicity not related to drug, resume at same dose or 1 dose lower**.
Grade 4	Discontinue vorinostat. However, if patient is clearly benefiting from treatment, may continue after recovery to \leq Grade 1 at PI's discretion.

*If optimally managed, patients requiring a delay of >2 consecutive weeks will discontinue vorinostat

**Patients requiring a dose reduction to below 100 mg daily of vorinostat at dose level -2 schedule will discontinue vorinostat permanently.

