Grade 2 Requires therapy or infusion interruption but responds promptly to symptomatic treatment (e.g., antihistamines, NSAIDs, narcotics, IV fluids); prophylactic medications indicated for ≤ 24 hrs	
Stop Infusion.
 
Additional appropriate medical therapy may include but is not limited to:
 
IV fluids Antihistamines NSAIDs Acetaminophen Narcotics
 
Increase monitoring of vital signs as medically indicated until the participant is deemed medically stable in the opinion of the investigator.
 
If symptoms resolve within 1 hour of stopping drug infusion, the infusion may be restarted at 50% of the original infusion rate (e.g. from 100 mL/hr to 50 mL/hr). Otherwise dosing will be held until symptoms resolve and the participant should be premedicated for the next scheduled dose.
 
Participants who develop Grade 2 toxicity despite adequate premedication should be permanently discontinued from further study drug treatment
	
Participant may be premedicated 1.5h (± 30 minutes) prior to infusion of pembrolizumab with:
 
Diphenhydramine 50 mg po (or equivalent dose of antihistamine).
 
Acetaminophen 500-1000 mg po (or equivalent dose of analgesic).

Grades 3 or 4 Grade 3: Prolonged (i.e., not rapidly responsive to symptomatic medication and/or brief interruption of infusion); recurrence of symptoms following initial improvement; hospitalization indicated for other clinical sequelae (e.g., renal impairment, pulmonary infiltrates) Grade 4: Life-threatening; pressor or ventilatory support indicated	
Stop Infusion.
 
Additional appropriate medical therapy may include but is not limited to:
 
Epinephrine** IV fluids Antihistamines NSAIDs Acetaminophen Narcotics Oxygen Pressors Corticosteroids
 
Increase monitoring of vital signs as medically indicated until the participant is deemed medically stable in the opinion of the investigator.
 
Hospitalization may be indicated.
 
**In cases of anaphylaxis, epinephrine should be used immediately.
 
Participant is permanently discontinued from further study drug treatment.
	No subsequent dosing

Appropriate resuscitation equipment should be available at the bedside and a physician readily available during the period of drug administration. For further information, please refer to the Common Terminology Criteria for Adverse Events v4.0 (CTCAE) at <http://ctep.cancer.gov>

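### Sections 7.2, 7.4 and 7.7.1 are not aligned on toxicity-driven treatment loss in the DLT period, so some patients who stop for toxicity are replaced and leave the MTD count

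*Combined protocol and SAP*

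**What the plan says.** The first primary objective in Section 3.1 is "To assess the safety and tolerability of vorinostat plus pembrolizumab therapy"; the second is to find the MTD and RP2D of vorinostat in the combination. Section 7.3 judges the MTD on evaluable subjects (fewer than 33% with DLT, at least six treated), and Section 7.1.2 applies this as at most 1 of 6. Section 7.1.2 also states: "Patients who are not evaluable for DLT will be replaced". The notes to Table 4 define an evaluable patient as one who is fully evaluable for toxicity or who has a DLT.

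Three sections bear on a patient who loses treatment because of toxicity during the 42-day DLT period:

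- Section 7.2 lists the DLT criteria. None refers to missed doses or to stopping a drug.
- Section 7.7.1 adds a criterion for vorinostat: "if a patient misses > 30% of the vorinostat doses due to toxicity, this will be considered a DLT".
- Section 7.4 replaces a patient who "Missed 30% or more doses of vorinostat during the DLT period (not due to DLT"), who did not receive pembrolizumab, or who has "Study drug discontinuation for any reason other than DLT during the DLT period". Of patients replaced for missed doses it says that they "will not be included in DLT analysis". Toxicity short of a DLT is not excepted from any of the three reasons.

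Table 8 in Section 7.10.1 requires one toxicity stop that 7.2 does not list: "Participants who develop Grade 2 toxicity despite adequate premedication should be permanently discontinued from further study drug treatment". Section 7.12 also treats DLT and other unacceptable toxicity as separate grounds for stopping.

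**The concern.** A patient who stops a drug for related toxicity without meeting a DLT criterion has shown something about tolerability, which is a primary objective. If that patient is replaced, removal from the evaluable set depends on the outcome being studied, and the newcomer starts with a clean record. The MTD rule works on six patients, so a single reclassified patient can decide whether a level passes. The RP2D that follows is given to an expansion cohort of 40.

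The sections also conflict on their face. A given amount of vorinostat lost to toxicity can count as dose-limiting, lead to replacement, or fall between the two limits, depending on which section is applied.

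**Working it through.** **The plan's own rule.** 1/6 = 16.7% is below 33%; 2/6 = 33.3% is not. Only 0 or 1 DLT in six qualifies, so Sections 7.1.2 and 7.3 agree.

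**Vorinostat doses in the window.** Table 3 gives levels 1 and 2 twice-daily dosing on days 1-5 and 8-12. Over two cycles that is 10 days × 2 doses × 2 cycles = 40 doses on 20 dosing days (days 1-5, 8-12, 22-26, 29-33). 30% of 40 is 12 doses, or 6 dosing days.

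For a permanent stop due to toxicity, with no other 7.2 criterion met:

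| Last dosing day | Doses missed | Section 7.7.1 | Section 7.4 |
|---|---|---|---|
| 24 or earlier | 35% or more | DLT | kept, since it is a DLT |
| 25 | 12/40 = 30% | not a DLT | replaced (bullets 1 and 3) |
| 26 | 10/40 = 25% | not a DLT | replaced (bullet 3) |
| 29 to 32 | 20% down to 5% | not a DLT | replaced (bullet 3) |

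A patient who misses exactly 12 scattered doses for toxicity, without stopping, also falls between the two limits. This tie cannot occur at level -1 (36 doses, 30% = 10.8) or level -2 (24 doses, 30% = 7.2), because those limits are not whole doses.

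**Pembrolizumab.** No section makes a toxicity-driven pembrolizumab stop a DLT. Under Table 8, a Grade 2 infusion reaction in cycle 1 that recurs despite premedication on cycle 2 day 1 (day 22) ends that treatment. It is not a DLT in 7.2 and leads to replacement under the third bullet of 7.4. This example assumes that vorinostat continues. If the study drug named in Table 8 means both agents, a vorinostat stop at day 22 misses 45% or more and 7.7.1 could apply. The text does not settle this.

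**Effect on one level.** Suppose a level has one DLT among six evaluable patients, and one patient was replaced for related toxicity. If that patient is put back as an event in place of a replacement without DLT, 1/6 becomes 2/6 and the level fails. If the replacement is kept as well, the figure is 2/7 = 28.6%, which is below the 33% in 7.3 but reaches the two-patient limit in 7.1.2. With no DLT, the patient put back gives 1/6 and the level still passes.

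**Probabilities.** Let d be the DLT rate and t the rate of related-toxicity stops that are not DLTs. The event rate is d/(1−t) when such patients are replaced and d + t when they are counted. With p the event rate, P(at most 1 of 6) = (1−p)^6 + 6p(1−p)^5. The documents give neither d nor t, so both are assumptions.

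| d | t | p replaced | P(at most 1/6) replaced | p counted | P(at most 1/6) counted |
|---|---|---|---|---|---|
| 20% | 0% | 0.200 | 0.655 | 0.20 | 0.655 |
| 20% | 1% | 0.202 | 0.650 | 0.21 | 0.631 |
| 20% | 2% | 0.204 | 0.645 | 0.22 | 0.606 |
| 20% | 5% | 0.211 | 0.630 | 0.25 | 0.534 |
| 20% | 10% | 0.222 | 0.601 | 0.30 | 0.420 |
| 15% | 5% | 0.158 | 0.758 | 0.20 | 0.655 |
| 15% | 10% | 0.167 | 0.737 | 0.25 | 0.534 |
| 10% | 5% | 0.105 | 0.875 | 0.15 | 0.776 |
| 10% | 10% | 0.111 | 0.863 | 0.20 | 0.655 |

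These describe one level with six evaluable patients, not the whole escalation path.

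**The case against.** Several stronger readings are tempting, and the documents do not support them.

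- A reader might infer that the MTD is judged only on patients who tolerated the drugs. It is not: patients with a DLT stay evaluable, and 7.7.1 already makes a DLT of any permanent toxicity stop of vorinostat with a last dosing day up to day 24. Vorinostat is also the only drug being escalated.
- A reader might infer that replacement understates the DLT rate. Against the plan's own endpoint it does the reverse, since d/(1−t) exceeds d (22% against 20% at t = 10%). The gap appears only against d + t, a broader endpoint that also counts toxicity stops.
- A reader might add recurrent Grade 2 pneumonitis from Table 5, or Grade 3 nausea and fatigue, as further foreseeable stops. Section 7.6.1.2 applies the Table 5 modifications after the DLT period. Section 7.2 exempts Grade 3 nausea and fatigue only when controlled, and a patient who stops permanently because of them is arguably not controlled.

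It is also fair to say that the frequency may be low. Section 4.4.5 reports drug-related discontinuation of 0% to 4.5% in pembrolizumab monotherapy trials, and infusion reactions in 2.5% of subjects in two of them. These figures are not limited to 42 days or to non-DLT events, and none is given for vorinostat stops, so they are only a guide. Section 7.3 lets the principal investigator choose an RP2D below the MTD on toxicity grounds. Section 11.1.2 summarises toxicities without excluding replaced patients, and Section 11.2 monitors unacceptable toxicity at the RP2D. Section 4.6.4 reports 42 patients already enrolled, with further accrual to the expansion cohort, so rewording 7.4 would not change a future escalation decision.

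These points narrow the concern but do not remove it. The sections still conflict, the safeguards do not enter the count that sets the MTD, and the past counts can still be examined.

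**Conclusion.** The concern holds in a limited form. As written, 7.4 removes from the MTD count patients whom 7.7.1 leaves just short of a DLT (exactly 12 of 40 doses missed for toxicity, or a vorinostat stop with a last dosing day from 25 to 32). It also removes patients who stop pembrolizumab for toxicity short of a listed DLT. They leave for reasons tied to tolerability, and counting them could only make a level look less tolerable.

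The size depends on how often this happens, which the documents do not say. At an assumed 20% DLT rate, P(at most 1/6) with replacement against counting is about 0.65 against 0.61 to 0.63 at 1% to 2% such stops, 0.63 against 0.53 at 5%, and 0.60 against 0.42 at 10%; near 0% there is no effect. The change from 1/6 to 2/6 needs a level with exactly one DLT and such a patient put back in place of a replacement without DLT. No sample size or power figure is affected.

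**What to change.** Reconcile Sections 7.2, 7.4 and 7.7.1: make the two 30% limits match, place the 7.7.1 rule in the DLT definition, and have 7.4 state how stops of either drug for related toxicity are handled. Which clinical rule applies is for the sponsor to decide. A reader might conclude that every possibly related toxicity stop has to become a DLT; the documents do not settle that, and this point does not ask for it.

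For the escalation levels, list every replaced patient with the reason. Beside each level's DLT count, report a sensitivity count that includes replaced patients who stopped or missed doses for related toxicity, stating whether their replacements stay in the denominator.

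The cost is a wording change and one extra table. The downside is that a level may look slightly less tolerable.

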7.5 Expansion Cohort

Once the RP2D has been determined, an expansion cohort of 40 patients will be enrolled and treated at the RP2D, to acquire additional safety and tolerability data about the combination. Toxicity monitoring will continue during the expansion segment. In addition, because of the unique immune-related adverse events (IrAEs) observed with checkpoint inhibitors, we will monitor for “unacceptable toxicity” with this new combination of drugs (defined in [Section10.2](#)). If >3 “unacceptable toxicity” events occur in the first 12 patients ($\geq 33\%$) treated (across disease subtypes) at RP2D, or at a rate $\geq 33\%$ thereafter at the quarterly review, we will halt accrual to fully evaluate these events and assess whether the regimen should be modified.

7.6 Study Treatment: Pembrolizumab

7.6.1 Dose Selection/Modification

7.6.1.1 Pembrolizumab Dose Selection

The rationale for selection of doses to be used in this trial is provided in Section 4.0 - Background and Rationale.

Details on preparation and administration of pembrolizumab (MK-3475) are provided in the Pharmacy Manual and Section 7.6.2.

7.6.1.2 Pembrolizumab Dose Modification (Escalation/Titration/Other)

Note: If pembrolizumab administration is held for toxicity, and the toxicity is most likely attributed to pembrolizumab and not attributed to vorinostat, administration of vorinostat can continue.

During the Phase I portion of the study, no intrapatient dose de-escalation will be allowed during the DLT period. After the DLT period, the following dose modifications are permitted for pembrolizumab-related adverse events according the guidelines outlined below in Table 5 for pembrolizumab. If, according to Table 5, pembrolizumab is discontinued permanently, the patient should continue to receive vorinostat.

Adverse events (both non-serious and serious) associated with pembrolizumab exposure may represent an immunologic etiology. These immune-related adverse events may occur shortly after the first dose or several months after the last dose of pembrolizumab treatment and may affect more than one body system simultaneously. Therefore, early recognition and initiation of treatment is critical to reduce complications. Based on existing clinical study data, most irAEs were reversible and could be managed with interruptions of pembrolizumab, administration of corticosteroids and/or other supportive care. For suspected irAEs, ensure adequate evaluation to confirm etiology or exclude other causes. Additional procedures or tests such as bronchoscopy, endoscopy, skin biopsy may be included as part of the evaluation. Based on the severity of irAEs, withhold or permanently discontinue pembrolizumab and administer corticosteroids. Dose modification and toxicity management guidelines for irAEs associated with pembrolizumab are provided in Table 5. See Section 7.10.1 for supportive care guidelines, including use of corticosteroids.

Table 5. Dose modification and toxicity management guidelines for immune-related AEs associated with pembrolizumab

General instructions:

1. Corticosteroid taper should be initiated upon AE improving to Grade 1 or less and continue to taper over at least 4 weeks.
2. For situations where pembrolizumab has been withheld, pembrolizumab can be resumed after AE has been reduced to Grade 1 or 0 and corticosteroid has been tapered. Pembrolizumab should be permanently discontinued if AE does not resolve within 12 weeks of last dose or corticosteroids cannot be reduced to ≤ 10 mg prednisone or equivalent per day within 12 weeks.
3. For severe and life-threatening irAEs, IV corticosteroid should be initiated first followed by oral steroid. Other immunosuppressive treatment should be initiated if irAEs cannot be controlled by corticosteroids.

Immune-related AEs	Toxicity grade or conditions (CTCAEv4.0)	Action taken to pembrolizumab	irAE management with corticosteroid and/or other therapies	Monitor and follow-up
Pneumonitis	Grade 2	Withhold	
 • Administer corticosteroids (initial dose of 1-2 mg/kg prednisone or equivalent) followed by taper 	
 • Monitor participants for signs and symptoms of pneumonitis • Evaluate participants with suspected pneumonitis with radiographic imaging and initiate corticosteroid treatment • Add prophylactic antibiotics for opportunistic infections
	Grade 3 or 4, or recurrent Grade 2	Permanently discontinue		

Diarrhea / Colitis	Grade 2 or 3	Withhold	
 Administer corticosteroids (initial dose of 1-2 mg/kg prednisone or equivalent) followed by taper 	
 Monitor participants for signs and symptoms of enterocolitis (ie, diarrhea, abdominal pain, blood or mucus in stool with or without fever) and of bowel perforation (ie, peritoneal signs and ileus). Participants with \geq Grade 2 diarrhea suspecting colitis should consider GI consultation and performing endoscopy to rule out colitis. Participants with diarrhea/colitis should be advised to drink liberal quantities of clear fluids. If sufficient oral fluid intake is not feasible, fluid and electrolytes should be substituted via IV infusion.
	Grade 4	Permanently discontinue		
AST / ALT elevation or Increased bilirubin	Grade 2	Withhold	
 Administer corticosteroids (initial dose of 0.5- 1 mg/kg prednisone or equivalent) followed by taper 	
 Monitor with liver function tests (consider weekly or more frequently until liver enzyme value returned to baseline or is stable
	Grade 3 or 4	Permanently discontinue	
 Administer corticosteroids (initial dose of 1-2 mg/kg prednisone or equivalent) followed by taper 	
Type 1 diabetes mellitus (T1DM) or Hyperglycemia	Newly onset T1DM or Grade 3 or 4 hyperglycemia associated with evidence of β -cell failure	Withhold	
 Initiate insulin replacement therapy for participants with T1DM Administer anti-hyperglycemic in participants with hyperglycemia 	
 Monitor participants for hyperglycemia or other signs and symptoms of diabetes.
Hypophysitis	Grade 2	Withhold	
 Administer corticosteroids and initiate hormonal replacements as clinically indicated. 	
 Monitor for signs and symptoms of hypophysitis (including hypopituitarism and adrenal insufficiency)
	Grade 3 or 4	Withhold or permanently discontinue ¹		
Hyperthyroidism	Grade 2	Continue	
 Treat with non-selective beta-blockers (eg, propranolol) or thionamides as appropriate 	
 Monitor for signs and symptoms of thyroid disorders.
	Grade 3 or 4	Withhold or permanently discontinue ¹		
Hypothyroidism	Grade 2-4	Continue	
 Initiate thyroid replacement hormones (eg, levothyroxine or liothyroinine) per standard of care 	
 Monitor for signs and symptoms of thyroid disorders.

Nephritis and Renal dysfunction	Grade 2	Withhold	
 Administer corticosteroids (prednisone 1-2 mg/kg or equivalent) followed by taper. 	
 Monitor changes of renal function
	Grade 3 or 4	Permanently discontinue		
Myocarditis	Grade 1 or 2	Withhold	
 Based on severity of AE administer corticosteroids 	
 Ensure adequate evaluation to confirm etiology and/or exclude other causes
	Grade 3 or 4	Permanently discontinue		
All other immune-related AEs	Intolerable/persistent Grade 2	Withhold	
 Based on type and severity of AE administer corticosteroids 	
 Ensure adequate evaluation to confirm etiology and/or exclude other causes
	Grade 3	Withhold or discontinue based on the type of event. Events that require discontinuation include and not limited to: Gullain-Barre Syndrome, encephalitis		
	Grade 4 or recurrent Grade 3	Permanently discontinue		

1. Withhold or permanently discontinue pembrolizumab is at the discretion of the investigator or treating physician.
 
NOTE: For participants with Grade 3 or 4 immune-related endocrinopathy where withhold of pembrolizumab is required, pembrolizumab may be resumed when AE resolves to \leq Grade 2 and is controlled with hormonal replacement therapy or achieved metabolic control (in case of T1DM).
				

Dosing interruptions are permitted in the case of medical / surgical events or logistical reasons not related to study therapy (e.g., elective surgery, unrelated medical events, patient vacation, and/or holidays). Subjects should be placed back on study therapy within 3 weeks of the scheduled interruption, unless otherwise discussed with the overall study PI. The reason for interruption should be documented in the patient's study record.

